## **INTRODUCTION:**

### **Aim and hypothesis**

We will conduct a randomized controlled trial (RCT) with economic evaluation investigating the clinical and cost-effectiveness of a physiotherapist-led strength exercise intervention compared to usual care as first-line treatment in patients with femoroacetabular impingement syndrome (FAIS). Furthermore, we will explore how exercise adherence and volume of a physiotherapist-led strength exercise intervention are associated with outcomes. We hypothesized that (i) 6-months of physiotherapist-led strength exercise intervention is superior (i.e.  $\geq 6$  points difference on the International Hip and Outcome Tool 33; iHOT-33), to usual care in improving hip related quality of life (QoL) in patients with FAIS after a 6 month intervention, (ii) 6-months of physiotherapist-led strength exercise intervention is cost-effective compared to usual first-line care at 12-months follow-up in patients with FAIS, and (iii) high exercise session adherence and high volume of exercise will be superior to low exercise adherence and low volume in moderating objectively- and patient-reported outcome measures in patients with FAIS.

## **STUDY METHODS**

### **Trial design**

The Better Hip trial is a multicenter, stratified (by hospital site), randomized (allocation 1:1), controlled, parallel-group, assessor-blinded, superiority trial conducted in Denmark (Aarhus, Horsens, Hvidovre, Aalborg, and Odense) and Australia (Melbourne).

### **Sample size calculation**

The sample size calculation is based on a clinical superiority calculation using data from a pilot RCT by Kemp et al. Kemp et al. found a mean change of 27 (SD 26) points on the iHOT-33 in their strength exercise group (e.g., intervention group) and a mean change of 11 (SD 8) points in their stretching group (e.g., control group) after 12 weeks of intervention (between-group difference of 16 [95% CI -9; 38] points). The superiority margin is a 6 points MCID in the between-group change on the iHOT-33. The estimated mean difference of 16 points, a superiority margin of 6 points, a SD of 19.2, a power of 80% and an alpha level of 5% results in a total sample size of n=94 (n=47 in each group). After allowing a dropout-rate of up to 28% our required sample size will be n=120 (n=60 in each group).

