## **Statistical interim analyses and stopping guidance**

No interim analysis or stopping guidance is planned as the interventions, supervised strength exercise, and usual care (e.g., advice to remain physically active following World Health Organization guidelines) are known to have minimal risks.

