#### *Dropouts:*

In instances where patients are not satisfied with how their treatment is progressing before reaching their individual goal, they will be able to have an additional consultation with their treating surgeon, where they will be treated in their best interests. There is a risk of dropout in both groups if the treatment results in insufficient improvement of symptoms. Dropout and the reason for dropout will be recorded throughout the study.

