## **Analysis methods**

### **Primary analysis**

#### *Intention-to-treat analysis:*

The primary analysis of clinical effectiveness will be the assessment of the between-group mean difference in change in hip-related QoL (iHOT-33) from baseline to 6 months after randomization. Between-group mean differences in change larger than 6.1 points will be considered clinically relevant. Consequently, to determine the intervention's effectiveness compared to usual care, the lower limit of the 95% confidence interval for the mean difference must be greater than 6.1 points. Secondary analysis will be the assessment of the between-group mean difference in change in secondary outcomes from baseline to 3 months, 6 months, and 12 months. Assessment of between-group differences in changes will be conducted using a linear mixed-effect model for continuous variables and a generalized linear mixed-effect model for binary variables. This approach accounts for the correlation between repeated measurements within the same patient over time. The model will include fixed effects for the intervention group (physiotherapist-led exercise or usual care) and time points (Baseline, 3, 6, and 12 months). Patients and recruitment sites (Aarhus, Aalborg, Hvidovre, Horsens, or Melbourne) will be included as random effects to account for potential clustering effects. To assess whether the effect of the intervention on hip-related QoL (iHOT-33) varies over time, an interaction term between the intervention group and time will be included. Supplementary, to further guide the clinical interpretation of change in iHOT-33, the between-group difference in the proportion of participants achieving the minimal clinically important difference of 6.1 for within-patient score change was analyzed using an a-priori threshold of 20%. A difference of less than 20% was considered no meaningful difference between treatments, and 20% or greater was considered a meaningful difference. A sensitivity analysis for thresholds of 10% and 30% will be conducted. Supplementary to this interpretation, we will conduct calculations for other identified values of minimal important change by Scholes et al., of 8.7 points, and Kemp et al., of 10.0 points.

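### The stated 80% power is not the power of the primary comparison: under the SAP's own 6.1-point confidence-interval rule it is about 70% at 47 per arm, and the control inputs come from a 12-week stretching arm, not from usual care at 6 months

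*SAP*

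**What the plan says.** The hypothesis is that the exercise programme is superior "to usual care in improving hip related quality of life (QoL) in patients with FAIS after a 6 month intervention" (SAP, Aim and hypothesis). The section on interim analyses illustrates the comparator as "usual care (e.g., advice to remain physically active following World Health Organization guidelines".

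The Sample size calculation section takes all its inputs from a pilot trial measured at 12 weeks. The exercise arm changed by 27 points (SD 26). The control figures are "a mean change of 11 (SD 8) points in their stretching group (e.g., control group) after 12 weeks of intervention". The calculation then uses "The estimated mean difference of 16 points, a superiority margin of 6 points", an SD of 19.2 and 80% power, and says that "an alpha level of 5% results in a total sample size of n=94 (n=47 in each group". The sidedness of alpha is not stated. Enrolment is then set at 120, 60 per group.

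The success rule is in the Intention-to-treat analysis section: "the lower limit of the 95% confidence interval for the mean difference must be greater than 6.1 points".

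**The concern.** The 80% is presented as the power of this trial, but the calculation differs from the primary analysis in two respects.

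First, the success rule. A lower 95% limit above 6.1 amounts to a one-sided 2.5% test against 6.1. The sizing appears to use a one-sided 5% test against 6.

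Second, the comparison. Stretching at 12 weeks stands in for usual care at 6 months. Both borrowed control figures matter: the change of 11 sets the assumed difference of 16, and the SD of 8 pulls the planning SD down from 26. The 12-week time point affects the exercise arm's 27 (SD 26) as well.

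What is at stake is how a miss is read. If the lower limit does not clear 6.1, a reader who trusts 80% power may take that as stronger evidence against a relevant benefit than the design can give.

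**Working it through.** **Inputs (SAP, Sample size calculation and Intention-to-treat analysis).** Exercise change 27, SD 26; control change 11, SD 8; margin 6 in the sizing and 6.1 in the success rule; 47 evaluable or 60 enrolled per arm.

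**The planning SD.** √((26² + 8²)/2) = √370 = 19.24, the plan's 19.2.

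**The plan's n.** The net difference is 16 − 6 = 10. By the normal approximation, n per arm = 2 × 19.2² × (z_α + 0.842)² / 10².

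- One-sided 5% (z = 1.645): 45.6, so 46 per arm. With margin 6.1 (net 9.9) it is 46.5, so 47. This matches the stated 47 to within one patient per arm.
- Two-sided 5% (z = 1.96): 57.9, so 58 per arm. This does not match.

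The stated n therefore corresponds to one-sided 5%.

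**Power formula.** Power = Φ[(27 − control change − margin)/SE − z], with SE = √((26² + SD_c²)/n).

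**Plan's inputs, 47 per arm.** SE = √(740/47) = 3.968.

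- Sizing rule (margin 6, z = 1.645): 10/3.968 = 2.520; Φ(0.875) = 80.9%. This reproduces the plan.
- Success rule (margin 6.1, z = 1.96): 9.9/3.968 = 2.495; Φ(0.535) = 70.4%.

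Moving only z from 1.645 to 1.96, with margin 6, gives 71.2%, so nearly all of the loss comes from the sidedness and little from the extra 0.1 point.

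**Plan's inputs, all 60 per arm evaluable.** SE = √(740/60) = 3.512. Success rule: 9.9/3.512 = 2.819; Φ(0.859) = 80.5%.

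**Range over usual care.** The SAP gives no usual-care figures, so the control values below are assumptions, apart from the pilot pair (SD 8, change 11). The SD ends are the plan's own 8 and 26, and exercise stays at 27 (SD 26). Power under the 6.1-point rule at 47 per arm:

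| Control SD | Change 5 | Change 8 | Change 11 | Change 13 |
|---|---|---|---|---|
| 8 | 98.0% | 90.2% | 70.4% | 51.2% |
| 26 | 84.2% | 67.2% | 45.5% | 31.3% |

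For SD 26, SE = √(1352/47) = 5.363. Change 11: 9.9/5.363 = 1.846; Φ(−0.114) = 45.5%. Change 5: 15.9/5.363 = 2.965; Φ(1.005) = 84.2%.

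With change held at 11, intermediate control SDs of 15 and 19.2 give 61.8% and 55.6%.

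These are change-score calculations, as in the plan. The planned mixed model may differ somewhat in efficiency, which the SAP's figures do not allow one to quantify.

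**The case against.** The strongest reply is that the SAP hides nothing. It names the pilot, the stretching arm, the 12 weeks and the wide pilot interval of −9 to 38. Borrowing from the nearest available trial is ordinary planning, and the reason for accepting stretching as a proxy may be given in the protocol. A power statement also changes neither the estimate nor the decision rule, and the SAP already requires a 95% confidence interval, which will show the precision achieved. All of this stands. It means that the choice of pilot is not itself an error and that the point concerns the stated figure and its interpretation.

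It does not rescue the 80%. The gap between the sizing rule and the success rule lies wholly within the SAP and needs no outside figure.

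A reader might go further and infer that the comparator mismatch leaves the trial with about 59% power. That number (58.7%) comes from the one-sided 5% sizing rule with the control SD raised to 26 while the borrowed change of 11 is kept. Under the same rule, SD 26 with a change of 5 gives 91.0%. Replacing one borrowed input and keeping the other is selective, and the SAP supports neither choice.

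Nor does the SAP show that usual care is the more variable arm. The text that dissatisfied patients may seek help, "they will be able to have an additional consultation with their treating surgeon, where they will be treated in their best interests", is not limited to one group, and hip surgery is recorded in both.

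**Conclusion.** The 80% is not the power of the primary comparison as the SAP defines it. With the plan's own inputs it is about 70% under the 6.1-point rule at 47 evaluable per arm, a shortfall of about 10 percentage points. It reaches about 80% only with no loss among the 60 per arm. This part rests on the SAP's figures, the normal approximation, and the inference that the unstated sidedness was one-sided because only that reproduces the n.

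The use of stretching at 12 weeks for usual care at 6 months adds uncertainty of unknown direction. Across the assumed values shown, power runs from about 31% to 98%. The documents do not support the conclusion that the mismatch by itself makes the trial underpowered, and no single lower figure should be attached to it.

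**What to change.** In the Sample size calculation section:

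1. Replace the 80% with the power of the planned n under the rule that the lower 95% limit exceeds 6.1: about 70% at 47 evaluable per arm with the pilot inputs, and about 80% if all 60 are evaluable. State the sidedness, and use 6.1 in place of the rounded margin in "The superiority margin is a 6 points MCID in the between-group change on the iHOT-33".
2. Add a two-way table of power over usual-care SD (8 to 26) and usual-care change (values below and above 11), labelled as assumptions.
3. Add a sentence saying that the pilot's 12-week exercise and stretching figures are a proxy for exercise and usual care at 6 months.

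The cost is a few lines of text and a short table. Enrolment, conduct and the decision rule stay as they are. The downside is a stated power that is lower and given as a range.

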## **STATISTICAL PRINCIPLES**

### **Confidence intervals and p-values**

Results will be expressed as between-group differences in means with 95% confidence intervals.

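### The 94 participants quoted for 80% power come from a one-sided 5% test; under the SAP's own 95% CI success rule the same number gives about 70%

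*SAP*

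**What the plan says.** The Sample size calculation section rests on "The estimated mean difference of 16 points, a superiority margin of 6 points", an SD of 19.2 derived from the pilot trial, 80% power and "an alpha level of 5"%. From these it reports that "a power of 80% and an alpha level of 5% results in a total sample size of n=94 (n=47 in each group"). It defines the margin as follows: "The superiority margin is a 6 points MCID in the between-group change on the iHOT-33". The enrolment target then comes from the dropout allowance: "After allowing a dropout-rate of up to 28% our required sample size will be n=120 (n=60 in each group").

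The rule for the primary conclusion is in the Intention-to-treat analysis section: "the lower limit of the 95% confidence interval for the mean difference must be greater than 6.1 points". The section on confidence intervals and p-values uses the same convention: "Results will be expressed as between-group differences in means with 95% confidence intervals". The SAP nowhere mentions a one-sided test, a 90% interval or a one-sided confidence bound.

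**The concern.** A sample size calculation should describe the test that decides the trial. Here the two differ. The calculation gives an alpha of 5% without its sidedness, and the success rule compares the lower limit of a 95% CI with a margin. On the usual two-sided reading of a 95% CI, that comparison has a one-sided error of 2.5%. If the 94 participants were found with 5% in one tail, the 80% belongs to a different, easier test.

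Two things are at stake. First, a trial that fails its primary criterion would be interpreted as if it had an 80% chance of detecting a true 16-point benefit, when the chance was lower. Second, an unresolved mismatch leaves room for argument once results are known. A result that clears a one-sided 5% rule but not the 95% CI rule could find support in the sample size section.

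**Working it through.** **Inputs, all from the SAP**
- Assumed difference 16, margin 6, SD 19.2, power 80%, alpha 5% (Sample size calculation).
- The SD is consistent with the pilot SDs given there: √((26² + 8²)/2) = 19.24.
- Allocation 1:1 (Trial design).
- Success rule: lower 95% confidence limit above 6.1 (Intention-to-treat analysis).
- Difference beyond the margin, δ: 16 − 6 = 10 in the calculation; 16 − 6.1 = 9.9 under the success rule.

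**Step 1. Reproduce the 47 per group**

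Normal approximation: n per group = 2 × [19.2 × (z_α + z_0.80) / δ]², with z_0.80 = 0.8416. The t-based figure is the smallest n at which the noncentral t distribution gives at least 80% power.

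| Test | δ | Normal approximation | t-test |
|---|---|---|---|
| One-sided 5% (z = 1.645) | 10 | 45.6, so 46 | **47** |
| One-sided 2.5% (z = 1.960) | 10 | 57.9, so 58 | 59 |
| One-sided 5% | 9.9 | 46.5, so 47 | 48 |
| One-sided 2.5% | 9.9 | 59.04, so 60 | 61 |

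The SAP's 47 is exactly the one-sided 5% t-test with δ = 10, where power is 80.5% (79.8% at 46). Ignoring the margin (δ = 16) gives 18 or 23 per group with the normal approximation. A version with unequal SDs of 26 and 8 gives 47 one-sided at 5% and 60 two-sided at 5%. Of the variants tried, only those with 5% in one tail give 47.

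**Step 2. Power of the rule that decides the trial**

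The lower 95% limit exceeds 6.1 when the t statistic against 6.1 exceeds its 97.5th percentile. At a true difference of 16 and SD 19.2:

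| Evaluable per group | Power, margin 6 | Power, margin 6.1 |
|---|---|---|
| 43 | 66.5% | 65.7% |
| 47 | 70.5% | 69.6% |
| 60 | 80.8% | 80.0% |

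The row for 43 is the SAP's own dropout case: 60 × (1 − 0.28) = 43.2. The last entry is 79.99% before rounding, so strictly 61 per group are needed for 80%.

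**Step 3. The same shortfall in iHOT-33 points**

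At 47 per group the standard error of the difference is 19.2 × √(2/47) = 3.96, and the 97.5th percentile of t on 92 degrees of freedom is 1.986. Success therefore needs an observed difference of at least 6.1 + 1.986 × 3.96 = 14.0 points. For 80% power at that size the true difference would have to be about 17.3 points, not 16.

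**Step 4. Which part matters**

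At 47 per group and margin 6, going from 5% to 2.5% in one tail takes power from 80.5% to 70.5%. Moving the margin to 6.1 takes it from 70.5% to 69.6%.

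**The case against.** - **The calculation contains no arithmetic error.** Ninety-four is right for a one-sided 5% test against a margin of 6. This is correct: the fault lies in the unstated sidedness and the mismatch with the success rule. The consequence is the same, because the 80% does not apply to the rule in use.
- **The trial randomises 60 per group, follows participants who stop the intervention and analyses everyone with the data collected, so 47 is only a planning figure.** This has force. With complete follow-up the rule has essentially 80% power, so the figure of 70% must be tied to 47 evaluable per group. But the SAP attaches its 80% to 94 participants and reserves the other 26 for dropout. At its stated 28% loss, power falls to about 66%.
- **The repeated-measures mixed model may be more efficient than a comparison of change scores.** Possibly, but the SAP does not quantify a gain and the calculation does not use one. To restore 80% at 47 per group with margin 6.1, the effective SD would have to fall from 19.2 to about 17.
- **The mismatch does not inflate the type I error, since the success rule is the stricter of the two.** True. The harm is confined to the stated power and to how a failed primary criterion is read.
- **The step from 6 to 6.1 looks like rounding.** Agreed; its effect is small and aligning it is editorial.

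**Conclusion.** The point holds. The sample size was found with a one-sided 5% test, the primary conclusion is decided by what amounts to a one-sided 2.5% test, and nothing in the SAP reconciles them. For the 94 participants to whom the SAP attaches 80% power, the power of its own rule is about 70%: 69.6% by the t-test and 70.5% by the normal approximation, both with margin 6.1. The chance of missing a true 16-point benefit is thus about 30%, not 20%. Power reaches 80% only if all 120 are evaluable.

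These figures take the SAP's difference and SD at face value, read the 95% CI as two-sided, and assume an unadjusted comparison of mean change between two equal groups.

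**What to change.** Keep the 95% CI rule and correct the power statement. Suggested wording for the Sample size calculation:

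> Success requires the lower limit of the two-sided 95% confidence interval to exceed 6.1 points. At a true difference of 16 points and an SD of 19.2, power is about 66% with 43 evaluable participants per group, 70% with 47 and 80% with 60. The figure of 47 per group was obtained with a one-sided 5% test and a margin of 6.

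Use 6.1 as the single margin in the hypothesis, the sample size section and the decision rule.

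The dropout sentence needs correcting in the same edit. A 28% loss from 120 does not leave 94: 94/0.72 = 130.6, so 131 would be needed, whereas 120 corresponds to 94 × 1.28 = 120.3. Going from 60 to 47 per group is a loss of 13/60 = 21.7%.

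The cost is SAP wording only. Enrolment, model and success criterion stay as they are. The price is a less favourable stated power, and the change should be made before anyone sees outcome data by group.

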### **Withdrawal/follow-up**

Participants deciding to withdraw from the intervention will be asked to complete outcome assessments even though they stop attending exercise sessions or receive hip surgery.

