The primary analysis and subsequent inferences will follow the intention-to-treat principle, which means that all participants will be analyzed in the groups to which they were originally randomized, regardless of their adherence to the assigned treatment.

Model validation will be performed by comparing observed and expected within-subject standard deviations and correlations and by inspecting plots of standardized residuals versus fitted values and QQ plots for the standardized residuals.

*Per protocol analysis:*

Supplementary to the intention-to-treat analysis a per protocol analysis will be conducted. This analysis will focus on participants who strictly adhere (i.e., > 75 % total number of sessions) to the assigned treatment protocol. It will provide additional insights into the treatment effect among participants who complied with the assigned intervention. Furthermore, a sub-analysis will exclude patients who have received hip surgery within 6 months of follow-up.

*Missing data*

No imputations will be applied in the primary analysis. Each randomized participant will be included in the intention-to-treat analysis with the data collected for the participant. An attempt to collect data from all randomized participants will be made, regardless of adherence to interventions.

*Outliers*

The dataset will be visually inspected and examined to identify outliers potentially caused by typographical errors. These outliers will be cross-referenced with other data sources (e.g., printed test schemes) or through discussion with the responsible outcome assessor. If confirmed, these outliers will be corrected to actual values. Alternatively, outliers will be removed from the dataset if there is confidence that they are data errors. A sensitivity analysis will be conducted to assess the impact of outlier handling decisions on the statistical analysis results. If the conclusions change substantially due to the exclusion of potential erroneous measurements (which are not confirmed), both conclusions will be reported; otherwise, only the conclusion from the analysis, including all data, will be presented.

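### The 120 patients planned do not cover 28% dropout: they keep the required 94 only up to 26 losses (21.7%)

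*SAP*

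**What the plan says.** All the figures at issue stand in the SAP under Sample size calculation. With a difference of 16 points, a margin of 6, an SD of 19.2, 80% power and 5% alpha, the calculation "results in a total sample size of n=94 (n=47 in each group"). The next sentence moves from patients needed to patients enrolled: "After allowing a dropout-rate of up to 28% our required sample size will be n=120 (n=60 in each group"). No inflation formula is given, and no other section defines the dropout rate on a different base.

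Two other places bear on what a dropout costs the analysis. Under Withdrawal/follow-up, participants who leave the intervention "will be asked to complete outcome assessments even though they stop attending exercise sessions or receive hip surgery". Under Missing data, the primary analysis uses no imputation, and "Each randomized participant will be included in the intention-to-treat analysis with the data collected for the participant".

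**The concern.** A dropout rate is ordinarily the share of randomized patients who are lost. To end with a required number after a loss rate d, that number is divided by (1 − d). Multiplying it by (1 + d) gives too few patients, and the gap widens as d grows. At 28% the difference is visible: 120 against 131 or 132.

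At stake is the tolerance that the trial states for itself. With 27 to 33 losses (22.5% to 27.5% of 120), the team could report attrition inside its planned allowance while holding fewer than the 94 patients it set as its requirement. The CONSORT flowchart planned in the SAP counts losses among those randomized, so readers will compare the 28% with 120, not with 94.

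**Working it through.** **Inputs** (SAP, Sample size calculation): required 94, 47 per group; enrolled 120, 60 per group; dropout up to 28%; expected difference 16; margin 6; SD 19.2; power 80%; alpha 5%, sidedness not stated.

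**Step 1: reproduce the 94.** The difference beyond the margin is 16 − 6 = 10. The normal formula is n per group = 2 × [SD × (z for alpha + z for power) / 10]².
- One-sided 5%: 45.6, so 46 per group. The t-test version gives 46.3, so 47 per group, which is the SAP's 94.
- Two-sided 5%: 57.9, so 58 per group (59 by t-test). This does not give 94.

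**Step 2: reproduce the 120.**
- 94 × 1.28 = 120.3, and 47 × 1.28 = 60.2. These match 120 and 60 after rounding down.
- 94 / (1 − 0.28) = 130.6. Per group, 47 / 0.72 = 65.3, so 66 per group and 132 in total. These do not match.

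The 26 extra patients are 26 / 94 = 27.7% of the completers but 26 / 120 = 21.7% of those enrolled. The printed figure is therefore consistent with taking 28% of the completers. As no formula is printed, that origin is an inference.

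**Step 3: what 120 supports.**
- After 28% loss: 120 × 0.72 = 86.4 (60 × 0.72 = 43.2 per group), about 8 short of 94.
- In whole patients: 28% of 120 is 33.6, so at most 33 losses lie inside the allowance. That leaves 87, which is 7 short.
- Losses that still leave 94: 120 − 94 = 26 (21.7%). To keep 47 in each group, neither may lose more than 60 − 47 = 13 (13 / 60 = 21.7%).

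**Step 4: effect on power.** Noncentral-t power with true difference 16 and SD 19.2, assuming that dropouts give no 6-month information:

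| Evaluable per group | Margin 6, one-sided 5% | Margin 6, two-sided 5% |
|---|---|---|
| 47 / 47 | 80.5% | 70.5% |
| 47 / 46 (27 losses) | 80.2% | 70.0% |
| 44 / 43 (33 losses) | 77.8% | 67.1% |
| 43 / 43 | 77.4% | 66.5% |

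Both columns are shown because the sample size section does not state sidedness. The loss due to dropout is the fall within a column, about 3 to 4 points. The gap between the columns exists before any dropout and is a separate matter. Under the decision rule in the primary analysis, that "the lower limit of the 95% confidence interval for the mean difference must be greater than 6.1 points", power falls by a similar amount, from 69.6% at 47 per group to 65.7% at 43.

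**The case against.** There are four fair points on the other side.

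- **The figures agree on another base.** If 28% is a share of the 94 completers, 94 and 120 are consistent. That stands as arithmetic. It is an unusual meaning for a dropout rate, however, and the SAP does not state it. On that reading the 28% still could not be compared with an observed dropout rate among 120 patients, so the sentence would need the same correction.
- **Dropping out of treatment is not the same as a missing outcome.** Participants who stop exercising or have surgery are still asked for assessments, and the mixed model uses whatever data are collected. This stands, and it makes the power losses above upper bounds if losses are about equal between groups. The SAP gives no figure to say how much is recovered, and its sample size calculation takes no credit for it.
- **A loss of 34, leaving 86, lies just outside the allowance.** Correct: the worst whole-number case inside it is 33 losses, leaving 87, with power of 77.8% instead of 77.4%. The conclusion is the same.
- **The effect is very small.** Also correct. With 27 losses split almost evenly, power is still 80.2% on the one-sided basis.

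The equal-loss assumption is only a convenience. Under Dropouts, the SAP says "There is a risk of dropout in both groups if the treatment results in insufficient improvement of symptoms" and does not apportion that risk.

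**Conclusion.** The statement is wrong as written: 120 patients retain the required 94 only up to 26 losses, a tolerance of 21.7% and not 28%. At the full 28% the trial would be about 8 patients short. That costs about 3 points of power on the one-sided 5% basis that reproduces the SAP's own 47 per group, or about 4 points at two-sided 5%.

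The sample size result assumes that the dropout rate refers to those randomized. The power figures also assume equal losses and no 6-month information from dropouts. The matter is minor: with 26 losses or fewer, and no more than 13 in either group, there is no shortfall, and the estimand, model, analysis set and decision rule are unaffected. Confidence in the arithmetic is high.

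**What to change.** Replace the sentence on dropout in the sample size section with one such as: n=120 (60 per group) allows for the loss of up to 26 patients (21.7% of those randomized), no more than 13 in either group, while retaining 94 evaluable (47 per group).

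This changes one sentence of the SAP. It needs no added enrolment, and no power figure has to be added to the sentence. The only cost is a stated dropout tolerance of 21.7% in place of 28%. Keeping the 28% on the usual base would instead require 132 patients in equal groups, 12 more than planned.
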